## 10.3 Reporting of Serious Adverse Events

The investigator should report all SAEs occurring during the treatment period (whether or not related to the IMP) within 24 hours of the site study team becoming aware of the event, to the Assign Safety Desk by completing an SAE Report Form.

The completed SAE Report Form should be submitted to the Assign Safety Desk either by fax or as pdf per e-mail:

Fax: 

Email 

For urgent questions, please call the 24-hours Safety Hotline: 

Under certain circumstances, the first notification can be done by phone, nevertheless, a written Serious Adverse Event Report Form should be submitted for confirmation to Assign Safety Desk.

After the initial SAE report the investigator will follow up proactively each subject and provide further information like copies of hospital case reports, laboratory reports or autopsy reports, to the Assign Safety Desk within 24 h after receipt.

Assign Safety Desk will assess initial and follow-up SAE reports from the site for expectedness, which will be determined based on the most recent edition of the Investigator's Brochure.

Reports of suspected unexpected serious adverse reactions (SUSARs) will be reported in an expedited manner to the CA as required per local regulations within the required time frame.

The original copy of the SAE Report Form and the fax confirmation sheet must be kept with the documentation at the study site. Each SAE has also to be documented in the eCRF as a serious adverse event in the corresponding AE section.

## 10.4 Follow-up of Adverse Events

During and following a subject's participation in a clinical trial, the investigator will ensure that adequate medical care is provided to the subject for any adverse events, including clinically significant laboratory values related to the trial.

All non-serious and serious adverse events will be followed until the subject has recovered, stabilised, recovered with sequelae or died until end of the study.

Follow-up information about a previously reported SAE must also be reported within 24 hours of the investigator receiving it. The initial SAE report form should be used, stating that this is a

follow-up report to the previously reported SAE and giving the number and date of the follow-up report. The information provided should describe whether the event has resolved or continues, if and how it was treated, and whether the subject continued or discontinued study participation, if not already stated in the initial report.

## 10.5 Reporting of SUSARs

A serious adverse reaction that is not expected according to the current IB and where the causality is assessed as "definitely", "probably" or "possibly", qualifies as "suspected" unexpected serious adverse reaction.

On behalf of the sponsor, Assign Safety Desk will be responsible to fulfil the requirements of expedited reporting of all SUSARs (suspected unexpected serious adverse reactions) to the Competent Authorities, Ethics Committees and principal investigators concerned according to national and European law and regulations.

For fatal and life-threatening SUSARs, this will be done no later than 7 calendar days after the sponsor or delegate is first aware of the reaction. Any additional relevant information to the initial report that was not available within the 7 calendar days will be reported within 8 additional calendar days. All other SUSARs will be reported within 15 calendar days.

Treatment codes will be unblinded for specific participants.

Principal investigators will be informed of all SUSARs related to the relevant IMP for all studies conducted with the same IMP, whether or not the event occurred in the current trial.

## 10.6 Reporting of Pregnancies

Women should not become pregnant during the treatment period of the study. If a subject becomes pregnant within the treatment period up to day 56, she should immediately inform the investigator about the pregnancy.

The investigator will complete a corresponding Pregnancy Report Form and send the form within 24 hours after becoming aware to Assign Safety Desk via fax or as pdf per e-mail:

Fax:

Email

The first notification can be done via phone 24-hours Safety Hotline:

A blue rectangular box with a thin black border, containing the text 'PPD' at the top right corner. The rest of the box is redacted.

Nevertheless, a written Pregnancy Report Form must be submitted for confirmation. The subject should attend follow-up visits as planned. In addition, participants who become pregnant within the treatment period up to day 56 (and who received at least one dose) will be followed until the pregnancy outcome, even if this occurs after the study is completed.

Pregnancy itself is not regarded as an AE unless there is a suspicion that the IMP may have interfered with the effectiveness of a contraceptive medication. However, the outcome of all pregnancies that begin before day 56 (spontaneous miscarriage, elective termination, normal birth or congenital abnormality) will be followed up and documented even if the subject was discontinued from the study.

A pregnancy outcome of a congenital abnormality/birth defect would qualify as an SAE and will be reported to Assign Safety Desk for processing to the regulatory authority. A pregnancy outcome of an elective abortion without evidence of complications would not be processed as an AE.

## **10.7 Development Safety Update Reports**

Assign Data Management and Biostatistics GmbH will submit a DSUR once a year throughout the clinical trial to the competent authority (AGES), ethics committee, according to applicable regulations and requirements.

## 11. ASSESSMENT OF SAFETY

Adverse event rates compared between 4 different treatment groups will be used to evaluate the secondary study objective. Please also refer to Table 2, summarising study procedures including safety assessments.

### 11.1 Safety Laboratory Parameter Assessments

Haematology, blood chemistry, coagulation parameters and urinalysis will be assessed for subject's safety at screening, Visit 2, Visit 4 and additionally at Early Termination (if applicable). Please refer to section 10.

### 11.2 Symptom-directed Physical Examination

A full physical exam will be performed at screening and a system based physical examination will be done, if necessary, according to findings in a symptom-directed physical examination at Visit 1,2 and 3. This means if a symptom is reported by the subject, a system-based assessment will be performed, if needed, for a detailed check of the affected body system.

Any symptom reported after first vaccination, including worsening of pre-existing conditions (i.e. medical history/concomitant diseases), will be recorded as AE.

### 11.3 System-based Physical Examination

All participants will undergo a system-based physical examination, including but not limited to assessment of general appearance and skin, head/eyes/ears/nose/throat, respiratory system, cardiovascular system, abdominal and gastrointestinal system, musculoskeletal system, neurological system and lymph nodes.

This system-based physical examination will only be performed if necessary, according to findings of the symptom-directed physical exam at Visit screening as well as Visits 1,2 and 3.

### 11.4 Vital Signs and Body Temperature

Systolic and diastolic blood pressure and pulse rate as well as body temperature will be recorded at screening and Visits 1,2 and 3 with the subject at rest in a sitting position.

### 11.5 Post Vaccination Reactogenicity Assessments

All participants enrolled in the study and who receive at least one study treatment (MV-ZIKA-RSP or placebo) will be followed up 28 days after each study treatment. Solicited and unsolicited AEs will be recorded at each visit until the end of the study at Visit 4.

## 11.6 Local and Systemic Tolerability

The local tolerability (i.e. injection site reactions) will be inspected and evaluated by the investigator one hour after each IMP administration.

Additionally, local tolerability (i.e. inspection of the previous injection site) will be assessed at the following visits and prior to application of the subsequent vaccination at Visit 2 (day 28). Furthermore, local tolerability will be evaluated by the participants in the subject diaries for 7 days starting 6 hours after each treatment.

The grading of local reaction will be performed by means of a stencil (provided to the subject as shown in Appendix 1) and per "Guidance for Industry: Toxicity Grading Scale for Healthy Adult and Adolescent Volunteers Enrolled in Preventive Vaccine Clinical Trials", modified, reflecting the guidance of the Brighton Collaboration (Table 5).

Findings in the local tolerability examination by the investigator as well as local tolerability findings recorded in the subject diary will be covered as adverse events in the eCRF.

## 11.7 Subject Diary

The participants will be instructed to complete a diary for 7 days after each vaccination to document local and systemic tolerability as well as body temperature.

Solicited local and solicited systemic AEs will be assessed by the participants themselves by checking for presence of the listed symptoms and measuring the size of the affected area where appropriate (a template will be provided for local reaction grading, as shown in Appendix 1). The diary will also provide space for recording unsolicited AEs and concomitant medication.

Recording should be done approximately at the same time each day, starting on the day of vaccination. The first entry should be made 6 hours  $\pm 1$ h after vaccination at Visit 1 and Visit 2.

The participants' diaries will be collected and verified for completeness by the investigator at Visit 2 and Visit 3. Any AE recorded in the subject diaries will be entered in the eCRF by the investigator or authorised delegates. The investigator will re-evaluate the severity of the reported local and systemic AEs according to the below Tables 5 and 6.

Diary solicited systemic AEs include nausea, vomiting, headache, and fatigue, also to be documented in the eCRF.

In addition, body temperature will be recorded daily for 7 days and fever will be graded by the investigator according to the FDA Guidance for Industry. For details see below Table 6. Table 5. Grading of local reactions

| Local reaction to injectable product | Mild (grade 1) | Moderate (grade 2) | Severe (grade 3) | Potentially life threatening (grade 4) |
|--------------------------------------|----------------|--------------------|------------------|--|
|--------------------------------------|----------------|--------------------|------------------|--|

|   |   |  |  |  |
|---|---|--|--|--|
| Pain                             | Does not interfere with activity            | Interfere with activity or repeated use of non-narcotic pain reliever  | Prevents daily activity or repeated use of non-narcotic pain reliever                    | Emergency room (ER) visit or hospitalisation |
| Tenderness                       | Mild pain to touch                          | Pain with movement   | Significant pain at rest   | ER visit or hospitalisation                  |
| Erythema/ Redness    | ≤ 5 cm                                      | 5.1–10 cm  | > 10 cm  | Necrosis or exfoliate dermatitis             |
| Induration/ Swelling | ≤ 5 cm and does not interfere with activity | 5.1–10 cm or interfere with activity                                   | > 10 cm or prevents daily activity   | Necrosis                                     |
| Itching                          | Does not interfere with activity            | Interferes with activity or repeated use of non-narcotic pain reliever | Prevents daily activity or repeated use of anti-inflammation and pain-relieving ointment | Emergency room (ER) visit or hospitalisation |

 In addition to grading the measured local reaction at the greatest single diameter, the measurement should be recorded as a continuous variable.

 Swelling should be evaluated and graded using the functional scale as well as the actual measurement.

Table 6. Grading of systemic reactions

| Systemic Reaction (General)  | Mild (grade 1)  | Moderate (grade 2)  | Severe (grade 3)  | Potentially life threatening (grade 4)                             |
|--|---|---|---|--|
| Nausea/ vomiting  | No interference with activity or 1-2 episodes/ 24 hours | Some interference with activity or >2 episodes/ 24 hours                                | Prevents daily activity, requires outpatient IV hydration                         | Emergency room (ER) visit or hospitalisation for hypotensive shock |
| Diarrhoea   | 2-3 loose stools or < 400 gms/ 24hours                  | 4-5 stools or < 400-800 gms/ 24hours  | 6 or more watery stools or >800 gms/ 24 hours or requires outpatient IV hydration | ER visit or hospitalisation  |
| Headache  | No interference with activity                           | Repeated use of non-narcotic pain reliever >24 hours or some interference with activity | Significant; any use of narcotic pain reliever or prevents daily activity         | ER visit or hospitalisation  |
| Fatigue   | No interference with activity                           | Some interference with activity   | Significant; prevents daily activity  | ER visit or hospitalisation  |
| Myalgia   | No interference with activity                           | Some interference with activity   | Significant; prevents daily activity  | ER visit or hospitalisation  |
| Illness or clinical AE (as defined according to applicable regulations) | No interference with activity                           | Some interference with activity not requiring medical intervention                      | Prevents daily activity and requires medical intervention                         | ER visit or hospitalisation  |
| Fever (°C)  | 38.0 - 38.4   | 38.5 - 38.9   | 39.0 - 40.0   | >40.0  |

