**Safety Analysis:**

MV-ZIKA was well tolerated in this population of healthy men and women. Adverse events were predominantly mild or moderate. Only one subject experienced a severe solicited AE (fever) and five participants experienced severe unsolicited TEAEs (dysmenorrhea, arthralgia, hyperbilirubinemia, hypercholesterolemia, hyperlipidaemia and hypertriglyceridemia); all were judged unlikely or not related to IMP. No AE was judged serious.

Overall, 36 (75.0%) participants reported 200 solicited AEs and 39 (81.3%) participants reported 126 unsolicited AEs (TEAEs). The proportion of participants that experienced solicited and unsolicited AEs were higher in Group D (placebo) (100% and 87.5%, respectively) than Total ZIKA (70.0% and 80.0%, respectively). Only the proportion of participants that experienced unsolicited AEs in Group C (three high doses of MV-ZIKA [ $6 \times 10^5$  TCID50/dose]; 100%) were higher than Group D (87.5%).

Solicited local AEs occurred more frequently in participants who received MV-ZIKA than those who received placebo; more participants in Group C experienced solicited local AEs than Group A and Group B in all categories. The most frequently reported solicited local AE was injection site tenderness, followed by injection site pain. Injection site edema occurred only in Group C.

Solicited systemic AEs occurred across all treatment groups. The most frequently reported AE was headache; although the proportion of participants who experienced headache in Group D (placebo) was notably higher than any MV-ZIKA treatment group (62.5% versus 12.5–43.8%). Adverse events of myalgia, limb discomfort, rash and fever were only reported by participants who received MV-ZIKA.

The most frequently reported unsolicited AEs were nasopharyngitis and headache; the frequencies of these in participants who received MV-ZIKA were similar or less than those observed in participants who received placebo. A number of AEs were reported by participants who received MV-ZIKA but were not reported by those who received placebo. Most notably, these included general disorders and administration site conditions, and musculoskeletal and connective tissue disorders. Diarrhea was reported only by participants who received three high doses of MV-ZIKA (Group C).

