Drug-related TEAEs were reported by 18 (37.5%) participants. The proportion of participants who experienced drug-related TEAEs was the highest in Group C (10 [62.5%]), although Total ZIKA showed the same percentage (37.5%) as placebo (37.5%) and no statistically significant

differences in AE rate were observed between any MV-ZIKA treatment group and placebo. The most frequently reported drug-related AE was diarrhea, which occurred only in Group C; five (10.4%) participants experienced six episodes. No subject who received single dose of MV-ZIKA or placebo experienced diarrhea. The second most frequently reported drug-related AE was vertigo, which was distributed evenly across groups (one each in Groups A, B and D).

The proportion of participants who experienced medically attended TEAEs was higher in Group D (50.0%) than any MV-ZIKA treatment group (25.0–31.3%) but no statistically significant differences in AE rate were observed between any MV-ZIKA treatment group and Group D. Overall, 15 (31.3%) participants experienced medically attended TEAEs. The most frequently reported were arthralgia, dizziness, abdominal pain upper, hepatic steaosis and oropharyngeal pain, each reported by two participants.

The proportion of participants who experienced TEAEs for which action was taken was notably higher in those who received placebo (87.5%) than MV-ZIKA (31.3–37.5%). There were statistically significant differences in AE rate in Group B versus Group D and Group C versus Group D. The most frequently reported AEs with action taken were nasopharyngitis (five [10.4%] participants) followed by headache (four [8.3%] participants). All participants who reported unsolicited AEs for which action was taken took medicines except one subject who had a broken tooth and received an amalgam filling, one subject where action taken was unknown and one subject who had increased liver values and was supervised by the general practitioner.

No trends or changes were observed in hematology, coagulation or urinalysis. A small increase in mean ALT was observed in Group C. Four participants had abnormal clinical laboratory evaluations that were considered to be of clinical relevance but unlikely related to the study drug.

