### 6.2.2 *Derivations and Definitions*

- All solicited and unsolicited Adverse Events up to Day 56 (Visit 3) will be analyzed for the preliminary analysis and all AE in the database for the Final Analysis. The following rules will be applied to identify AEs up to Day 56 for preliminary analysis: In general, all AE with start date prior to or at Visit 3 are considered. If a subject has no Day 56 visit (Visit 3) then all AEs within 56 days from Visit 1 (Day 0) (Visit 1 + 56 days) are included. If start date of AE is incomplete (e.g. missing start day) and the AE could theoretically be within Visit 3, or if Visit 3 is not available, within 56 days from Visit 1 (Visit 1 + 56 days), it will be handled as AE up to Day 56 (Visit 3) and thus be included in the preliminary analysis. If start date of AE is unknown it will be handled as AE up to Day 56 visit (Visit 3) and thus be included in the preliminary analysis.
- Percentages for AE rates are based on N (treatment group totals).
- An Adverse Events is considered to be related to study treatment if “Relationship to Study Treatment” is answered with “definitely”, “probably” or “possibly” or the causality is missing.
- Tables showing “severe” events will include events with grade 3 or 4 or missing grade.
- In tables showing subjects with AEs by maximum severity, subjects will be counted only in the highest grading category (=“potentially life threatening”), but events will be counted in each reported grading category.

Adapted from:

STAT03\_A Statistical Analysis Plan

Version 6.0, Effective Date 16-Feb-2018

Confidential and intellectual property of Assign DMB. No part of this document or its contents may be duplicated, referenced, published or otherwise disclosed in any form or by any means without prior written consent of Assign DMB.

- In tables showing AEs by causality, subjects will be counted only in the strongest relationship category ("definitely"), but events will be counted in each category.

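### Table 5 uses the same analgesic criterion for grade 2 and grade 3 injection-site pain, so some reports cannot be classed as severe or not; the solicited systemic list is also left undefined

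*Combined protocol and SAP*

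**What the plan says.** **Pain grading.** In protocol 11.7, Table 5, moderate (grade 2) injection-site pain is "Interfere with activity or repeated use of non-narcotic pain reliever" and severe (grade 3) is "Prevents daily activity or repeated use of non-narcotic pain reliever". The investigator re-evaluates diary reports against Tables 5 and 6. SAP 6.2.2 states that tables of severe events "will include events with grade 3 or 4 or missing grade", and it counts each participant once, at the highest grade, in the maximum-severity tables. SAP 2.6 applies an overall Fisher-Freeman-Halton test to every adverse event table.

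**Solicited systemic symptoms.** Protocol 11.7 says: "Diary solicited systemic AEs include nausea, vomiting, headache, and fatigue, also to be documented in the eCRF". Body temperature is recorded separately. Table 6 grades these symptoms and also diarrhoea and myalgia. The SAP tabulates solicited systemic events by symptom (Tables 1.4.1.9 and 2.4.1.9) without saying which symptoms they are. One individual stopping criterion in protocol 8.9.1 is confined to grade 4 reactions that are solicited and systemic.

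**The concern.** Safety and tolerability are the primary objective, and tolerability is one of the inputs to the dose assessment in protocol 5.2. With 8 to 14 participants per arm, the severity tables carry much of that evidence. If one report satisfies two adjacent grades, and the boundary between them is also the boundary for severe, two careful raters can follow the plan exactly and produce different severe counts. Injection-site pain is not a marginal row: in the predecessor MV-ZIKA trial it was the second most frequent solicited local event (protocol 4.4.1).

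The open symptom list raises a smaller, separate question. It decides which symptoms participants are prompted for, which table an event enters, and which events the stopping criterion covers. The predecessor summary gives a reason to care about the two symptoms that 11.7 does not name. On myalgia it says "Adverse events of myalgia, limb discomfort, rash and fever were only reported by participants who received MV-ZIKA"; on diarrhoea, "The most frequently reported drug-related AE was diarrhea, which occurred only in Group C".

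**Working it through.** The documents give no sample-size, power or alpha figure bearing on this point, so there is no planned number to reproduce. The check is mainly textual, with arithmetic to show scale.

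**1. The two pain cells.** Each has two alternatives joined by *or*.
- Activity: interference at grade 2, prevention at grade 3. These differ.
- Analgesic: repeated non-narcotic use at both grades. These are identical.

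A report with repeated non-narcotic use and activity not prevented therefore meets both definitions.

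**2. Other rows.** Tenderness, erythema and induration have distinct grades. Itching at grade 3 changes the treatment alternative to "Prevents daily activity or repeated use of anti-inflammation and pain-relieving ointment", so it does not repeat grade 2. Headache in Table 6 reserves narcotic use for grade 3: "Significant; any use of narcotic pain reliever or prevents daily activity". Only the pain row overlaps.

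**3. Rules that might settle it.**
- Protocol 10.1.7 ties severe to incapacity or prevented activity, which points towards grade 2. But it then refers the rater to Table 5.
- Protocol 10.2 records the highest severity, which points towards grade 3. But it is written for an event whose severity changes over time.
- The worst-case rule (protocol 12.7, SAP 2.8) covers missing severity, not a severity that fits two grades.

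The first two pull in opposite directions and none applies on its terms.

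**4. Size.** Let s be an arm's unambiguous severe-pain count and k its number of participants whose severe status rests on the analgesic alternative alone. The reported count can lie anywhere from s to s + k. Arm sizes are 14, 14, 12 and 8 (protocol Table 1), so one participant moves the rate by 1/14 = 7.1, 1/12 = 8.3 or 1/8 = 12.5 percentage points. The values of k below are assumptions, with s = 0 throughout.

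| k in A/B/C/D | Severe, all graded 2 | Severe, all graded 3 | Overall exact p, all graded 3 |
|---|---|---|---|
| 1/1/1/0 | 0 in every arm | 7.1 / 7.1 / 8.3 / 0% | 1.00 |
| 3/1/1/0 | 0 in every arm | 21.4 / 7.1 / 8.3 / 0% | 0.563 |
| 5/2/2/0 | 0 in every arm | 35.7 / 14.3 / 16.7 / 0% | 0.247 |
| 7/1/1/0 | 0 in every arm | 50.0 / 7.1 / 8.3 / 0% | 0.006 |

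The descriptive rates move in every scenario; the test result changes only in the most extreme.

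**5. Primary endpoint.** Protocol 6.2.1 counts any adverse event to day 56. Neither grade nor solicited status enters, so it is the same in every row above.

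**6. The symptom list.** Section 11.7 names nausea, vomiting, headache and fatigue; Table 6 adds diarrhoea and myalgia; the SAP names none. The wording in 11.7 is inclusive rather than exhaustive, so the three places do not fix one set.

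**7. The predecessor signal.** Group C size: 10 participants were 62.5%, so 10/0.625 = 16. Placebo size D: solicited events occurred in 36 of 48 overall, 100% of placebo and 70% of vaccinees, so D + 0.70(48 − D) = 36 and D = 8. Drug-related diarrhoea was 5/16 = 31.3% in Group C against 0/8 on placebo, Fisher p = 0.13.

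**The case against.** The strongest reply is that the defect is narrow. The activity alternative still separates the grades, and the overlap bites only when analgesic use is repeated and activity is not prevented. The number of such reports may be zero. This stands, and it limits the point. A reader might infer that the trial's severe-reaction counts are arbitrary in general. The documents do not support that: every other row has usable grades, and only pain and the summary rows that pool it are touched.

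It can also be said that graders by convention take the highest grade met. That would leave the analgesic alternative at grade 2 with no function, and it is not written down for this situation.

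On the symptom list, a reader might infer that diarrhoea and myalgia are not solicited and depend on recall at day 28 or 56. Neither is established. The diary form is not in the documents, and 11.7 does not present its list as complete. Participants are asked to enter any adverse event for 7 days after each injection, the diary has space for unsolicited events, there is a day-7 call after the first dose, and staff ask at visits. Unlisted symptoms would be recorded, though perhaps in a different table.

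The predecessor evidence is also weaker than it looks. It concerns another product. Diarrhoea arose at three doses of 6×10^5 TCID50, while three doses of 1×10^5, this trial's high-dose level, produced none. It was described among the unsolicited events, so that route did detect it. No count is given for myalgia, and vaccinees outnumbered placebo recipients 40 to 8. Finally, the other individual criteria in protocol 8.9.1 do not depend on solicited status.

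**Conclusion.** The pain row is wrong as written. For reports that meet only the shared analgesic alternative, the SAP's severe-pain, severe-local, any-severe and maximum-severity results are undetermined within the bounds s to s + k. The any-AE primary endpoint and the other graded reactions are unaffected. The practical size depends on k, which the documents do not give; the scenarios above are illustrations, not forecasts. The predecessor's single participant with a severe solicited event among 48 suggests that severe counts may be small, but its grading scale is not described and the figure should not be carried over.

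The secondary conclusion is that solicited status is undefined for diarrhoea and myalgia. This affects the SAP's split between solicited and unsolicited tables and the scope of the grade 4 criterion in protocol 8.9.1. It does not show that either symptom went uncollected.

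The documents do not reveal which pain cell was intended. The revision index says the local grading was updated to match external guidance, section 11.6 calls the scale modified, and that guidance is not part of the documents.

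**What to change.** **Pain.** Reconcile the two cells so that no report can meet both grades, and record the change in the protocol and SAP. Identify pain events graded 2 or 3 in which non-narcotic analgesics were used repeatedly, and have them re-graded by assessors blind to arm. SAP 2.4 unblinds sponsor and data-management staff at the preliminary analysis, and SAP 2.1 describes that analysis as already past, so those staff should not do it. Use source diaries and the concomitant medication records. The adverse event fields listed in protocol 10.2 do not include activity limitation, so some events may stay unresolved. For those, report severe-pain and severe-local counts twice: all as grade 2, and all as grade 3.

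**Symptom list.** Reconcile 11.7, Table 6 and the SAP to one closed list of solicited systemic symptoms, and reconcile the stopping criterion in 8.9.1 with it. Changing the diary is too late for participants who have completed it. Instead, add a table by arm and by dose of diarrhoea and myalgia with onset within 7 days of an injection, whether recorded as solicited or unsolicited. Unsolicited tables by preferred term and listings with start dates are already planned, so only the seven-day cut and the pooling are new.

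**Cost.** One corrected table row, one agreed list, a small amount of blinded re-grading and one or two extra tables.
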